4.4.2 Secondary Efficacy Variables

Secondary efficacy variables of the study are listed below.

4.4.2.1 Corneometer measurements at other time points

The change from baseline in Corneometer measurements at 1 and 3 hours following the first product application as well as at Weeks 1, 4 and 8 are secondary variables which will be summarized by age strata, treatment regimen and study visit (Table 14.2.2.2, 14.2.2.3 for the ITT population and Table 14.2.1.5, 14.2.1.6 for the PP population).

4.4.2.2 Sebumeter and sebum excretion rate

The sebumeter measurement of each subject at each visit will be calculated as the mean of the three repeated assessments of the subject at that visit. The sebum excretion rate of each subject at each visit will be calculated as the difference of sebumeter kinetic measurement 90 mins post forehead cleansing to 5 mins post forehead cleansing. The sebumetry and sebum excretion rate changes from baseline at Weeks 1, 4 and 8 are secondary variables which will be summarized by age strata, treatment regimen and study visit (Table 14.2.3.2, 14.2.3.3 for sebumeter and Table 14.2.4.2, 14.2.4.3 for sebum excretion rate, ITT population).

4.4.2.3 Blemish counts

Clinical assessment of blemish counts (papules and pustules) change from baseline at Weeks 1, 4 and 8 are secondary variables which will be summarized by age stratum, treatment regimen and study visit (Table 14.2.5.2, 14.2.5.3 for the ITT population and Table 14.2.5.5, 14.2.5.6 for the PP population).

4.4.2.4 Lay person assessment

The lay person assessment resulting from the ranking of blemish images (Week 8 image vs. Baseline image with judgement either 'Week 8 is better' or 'Baseline is better') is a secondary variable. The assessment will be performed using polarised images and non-polarised images separately by 24 raters. Summary statistics will be provided by treatment (Table 14.2.6.2, for polarized image, Table 14.2.7.2 for non-polarised image, ITT population).

4.4.3 Handling of Missing Values/Censoring/Discontinuations

Missing data will not be replaced or imputed. Dropouts will be included in analyses up to the point of discontinuation.

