9.2.4. Handling of Dropouts and Missing Data

Missing data will not be replaced or imputed. Dropouts will be included in analyses up to the point of discontinuation.

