4.4.1 Primary Efficacy Endpoint

4.4.1.1 Primary Efficacy Endpoint Definition

The corneometer measurement of each subject at each assessment point will be calculated as the mean of the three repeated measurements of the subject at that assessment point.

The primary endpoint is the change from baseline in Corneometer measurement at 8 hours following the first product application. Data for the endpoint will be summarized by age stratum and treatment regimen (Table 14.2.2.2, 14.2.2.3 for the ITT population and Table 14.2.2.5, 14.2.2.6 for the PP population).

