4.5 Analysis of Secondary Objectives

4.5.1 Efficacy

The change from baseline in corneometer measurements at 1 and 3 hours following the first product application as well as at Weeks 1, 4 and 8 will be analysed at each post-baseline time point using the same ANCOVA model as in primary analysis. Differences between least squares means for (i) test product and no treatment regimen; (ii) positive control and no treatment regimen will be presented, together with 95% confidence intervals. The normality assumption for ANCOVA will be checked. If violated, non-parametric method such as Wilcoxon rank sum test may be applied.

The sebumeter and sebumeter excretion rate changes from baseline at Weeks 1, 4 and 8 will be analysed at each post-baseline visit using ANCOVA with treatment main effect, age stratum (<21, ≥21 years of age) and baseline count as covariate. Differences between least squares means for (i) test product and no treatment regimen; (ii) positive control and no treatment regimen will be presented, together with 95% confidence intervals (Table 14.2.3.1 for sebumeter, Table 14.2.4.1 for sebumeter excretion rate). The normality assumption for ANCOVA will be checked. If violated, non-parametric method such as Wilcoxon rank sum test may be applied.

Clinical assessment of blemish counts (papules and pustules) change from baseline at Weeks 1, 4 and 8 will be analysed at each post-baseline visit using ANCOVA with treatment main effect, age stratum (<21, ≥21 years of age) and baseline count as covariate. Differences between least squares means for (i) test product and no treatment regimen; (ii) positive control and no treatment regimen will be presented, together with 95% confidence intervals (Table 14.2.5.1 for the ITT population and Table 14.2.5.4 for the PP population). The normality assumption for ANCOVA will be checked. If violated, non-parametric method such as Wilcoxon rank sum test may be applied. A figure will be provided for blemish profile of the ITT population (Figure 14.2.1).

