The summary and analysis of lay person image assessment will be performed for polarised images and non-polarised images separately. Proportion of subjects evaluated as 'Week 8 is better' will be tabulated by treatment group and rater. Data from all 24 raters will also be pooled and a repeated measure logistic regression will be applied including effects of treatment and age stratum and exchangeable correlation structure among repeats. Odds ratio between (i) test product and no treatment regimen; (ii) positive control and no treatment regimen will be provided together with its 95%CI (Table 14.2.6.1 for polarised image, Table

14.2.7.1 for non-polarised image). This analysis will not be performed if all subjects are judged by all raters as 'Week 8 is better'.

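### Week 8 comparisons come from separate by-visit ANCOVAs that discard the Week 1 and Week 4 data of subjects who left; one repeated-measures model per endpoint would be a cheap improvement

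*SAP*

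**What the plan says.** **Missing data.** SAP 4.4.3: "Missing data will not be replaced or imputed. Dropouts will be included in analyses up to the point of discontinuation". Protocol 9.2.4 has the same rule: "Missing data will not be replaced or imputed".

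**Model.** In SAP 4.5.1 the later Corneometer values "will be analysed at each post-baseline time point using the same ANCOVA model as in primary analysis". Sebumeter, sebum excretion rate and blemish counts each get the same treatment: change from baseline at Weeks 1, 4 and 8 "will be analysed at each post-baseline visit using ANCOVA with treatment main effect", plus age stratum and baseline. A Wilcoxon test may be used if normality fails.

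**Population.** Efficacy is analysed on the ITT set, which needs only one post-baseline efficacy assessment (SAP 4.1.3). A subject who leaves after Week 4 is in the ITT set but cannot enter a Week 8 model.

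**Lay-person endpoint.** Week 8 photographs are analysed by a "repeated measure logistic regression will be applied including effects of treatment and age stratum and exchangeable correlation structure among repeats". The repeats are the 24 raters, not visits.

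**Primary endpoint.** SAP 4.4.1.1: "The primary endpoint is the change from baseline in Corneometer measurement at 8 hours following the first product application".

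**Dropout.** The sample size sections (Protocol 9.1, SAP 1.4) assume 10% overall. Protocol 4.5 allows no replacement. No rate by arm is given. Neither document plans a model across visits or a missing-data sensitivity analysis. The per-protocol analysis addresses deviations, not missing values.

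**The concern.** A subject who leaves between Week 4 and Week 8 has baseline, Week 1 and Week 4 values on file, and the Week 8 analysis uses none of them. If leaving is related to how the skin has been doing since baseline, the subjects left at Week 8 are a selected group, and the selection need not be equal across arms.

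Such a link is plausible here, although nothing in the documents shows it. Only evaluators are blinded (Protocol 5.7.2). Untreated subjects use cleanser alone and accept tight limits on other facial products for eight weeks (Protocol 3.2, 5.2).

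At stake are the Week 8 estimates for blemish counts, oiliness and sustained moisturisation. Protocol 9.2 and SAP 4.4 say the results will inform the sizing of later studies, so the point estimates matter more than the p-values.

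**Working it through.** **1. The plan's own figures, for scale.**
- Inputs (Protocol 9.1): 132 randomised, 40 completers per arm, difference 0.6 SD, two-sided alpha 0.05, power about 80%. Equal allocation (44 per arm) is inferred.
- Completers: 44 x 0.9 = 39.6 per arm, which agrees with 40.
- Power = Phi(0.6/sqrt(2/n) - 1.96). For n = 40: Phi(2.683 - 1.960) = 76.5%. For n = 44: Phi(2.814 - 1.960) = 80.4%. The stated power matches the number randomised, not the completers. That is a separate matter, and nothing below depends on it.
- Unadjusted SE of the difference at 40 per arm: sqrt(2/40) = 0.22 SD.

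**2. Simulation set-up.** Everything here beyond the 0.6 SD, the 44 per arm and the 10% is an assumption.
- Treated-minus-untreated effect at Week 8: -0.60 SD (negative is better).
- Dropout occurs between Week 4 and Week 8, 10% on average over the two arms.
- Correlations between baseline and visits: 0.5 to 0.7.
- Under missing at random (MAR), the chance of leaving is proportional to exp(b x Week 4 value). With b = 0.5 the weight rises 1.6-fold per SD; with b = 1.5 it rises 4.5-fold.
- Planned analysis: regress Week 8 on arm and baseline among subjects with a Week 8 value.
- Comparator: the likelihood estimate an MMRM would give. Regress Week 8 on arm, baseline, Week 1 and Week 4 in observed subjects, predict for all, then contrast the arms.

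**3. Week 8 estimate under MAR (true value -0.60).**

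| Dropout untreated / test | b | By-visit ANCOVA | MMRM |
|---|---|---|---|
| 10% / 10% | any | -0.60 | -0.60 |
| 15% / 5% | 0.5 | -0.58 | -0.60 |
| 15% / 5% | 1.0 | -0.56 | -0.60 |
| 15% / 5% | 1.5 | -0.55 | -0.60 |
| 20% / 0% | 0.5 | -0.56 | -0.60 |
| 20% / 0% | 1.0 | -0.52 | -0.60 |
| 20% / 0% | 1.5 | -0.49 | -0.60 |

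Attenuation runs from 0.60 - 0.58 = 0.02 to 0.60 - 0.49 = 0.11 SD. The simulated SE is about 0.20 for ANCOVA and 0.195 for MMRM. With uniform correlations of 0.5 or 0.7 the bias is smaller: about 0.01 and 0.03 SD at b = 0.5, and 0.03 and 0.06 SD at b = 1.5.

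**4. What triggers bias.** From large-sample runs with visit correlations of 0.4 to 0.8:
- Rates differ by arm, but dropout is random or depends on baseline only: bias 0.00 for both methods.
- Equal 10% rates, but the Week 4 dependence has opposite sign in the two arms: ANCOVA biased by 0.05 to 0.07 SD, MMRM 0.00.
- More loss in the test arm (15% against 5%, dependence in the same direction): the sign reverses and the effect is overstated by 0.02 to 0.03 SD. MMRM 0.00.

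**5. Missing not at random (MNAR).** Here dropout depends on the unseen Week 8 value.
- 15% / 5%: ANCOVA bias 0.04 to 0.10 SD, MMRM 0.03 to 0.09 SD.
- 20% / 0%: ANCOVA 0.09 to 0.21 SD, MMRM 0.07 to 0.19 SD.
- In a stronger 15% / 5% case the estimates were -0.51 and -0.54, so MMRM kept 0.06/0.09, or two thirds, of the bias.

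**6. Consequence for later sizing.** Required N scales as 1/effect squared. An estimate of -0.58 in place of -0.60 inflates N by (0.60/0.58)^2 = 1.07, and -0.49 by (0.60/0.49)^2 = 1.50. For comparison, a sampling error of one SE (0.2 SD) gives (0.60/0.40)^2 = 2.25.

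**The case against.** The other side has a good case. By-visit available-case ANCOVA is prespecified consistently in both documents, and preferring an MMRM does not make it an error. The model already adjusts for baseline and age stratum, so dropout explained by those does no harm. The study is exploratory: p-values serve as summaries, success means at least a favourable trend (Protocol 9.2.3), and the primary endpoint is measured on Day 1. The largest figure, 0.11 SD, needs strong dependence together with 20% loss in one arm and none in the other. If both arms truly lose 10%, a gap of nine or more out of 44 in that direction has probability about 0.1%.

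Nearly all of this stands, and it limits the point to an improvement. Two qualifications remain. First, the bias is not always towards zero: if the test arm loses more subjects with worse skin, the planned analysis overstates the effect. Second, the exploratory status lowers the cost of a wrong p-value but not of a distorted estimate carried into later sizing.

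A reader might infer that different dropout rates by arm are enough to bias Week 8. Step 4 shows they are not. A reader might also infer that any dependence on earlier values invalidates the analysis. The equal-rate row in step 3 shows no bias when rate and dependence are the same in both arms.

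**Conclusion.** The point holds as a modest, inexpensive improvement. For Corneometer at Weeks 1, 4 and 8, Sebumeter, sebum excretion rate and blemish counts, the plan discards collected data that could protect the Week 8 comparison. Bias needs two conditions: dropout related to post-baseline values beyond baseline and age stratum, and a difference between arms in either the rate or that relation.

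Under the MAR scenarios with more untreated loss, the attenuation is about 0.02 to 0.11 SD of a 0.60 SD effect (3% to 18%), at most about half an SE. Arm-specific rates, mechanism, correlations and the Week 8 effect are all assumed. The documents supply only the overall 10% dropout and the 0.6 SD planning difference.

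Two stronger readings are not supported. The documents give no ground for saying that the Week 8 results are biased, since no mechanism or rate by arm is stated. Nor would a repeated-measures model settle the matter: under MNAR it keeps roughly two thirds to nine tenths of the bias. The Day 1 primary analysis is untouched, and the lay-person endpoint has a single post-baseline time point, so a model across visits recovers nothing there.

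**What to change.** In SAP 4.5.1, fit one MMRM per endpoint over Weeks 1, 4 and 8 for Corneometer, Sebumeter, sebum excretion rate and blemish counts.
- Terms: treatment, visit, treatment-by-visit, age stratum, baseline and baseline-by-visit.
- Covariance: unstructured, with a fallback structure named in advance in case of non-convergence.
- Output: the same least-squares-mean contrasts at each visit (test against no treatment, positive control against no treatment).
- Keep the by-visit ANCOVA, with its Wilcoxon option, as a sensitivity analysis.
- Report Week 8 missingness by arm and reason, because the MMRM result depends on MAR.
- Leave the Day 1 primary ANCOVA and the lay-person analysis as they are.

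SAP Addendum 1 records that its own extra analysis was requested after unblinding. If the MMRM is also added at that stage, it should enter by addendum as a labelled sensitivity analysis beside the prespecified ANCOVA.

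The cost is some SAP wording, a standard SAS procedure and a few extra tables. No new data are needed, and precision was the same or slightly better in the simulations. The one technical burden is the fallback covariance.

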4.5 Analysis of Secondary Objectives

4.5.1 Efficacy

The change from baseline in corneometer measurements at 1 and 3 hours following the first product application as well as at Weeks 1, 4 and 8 will be analysed at each post-baseline time point using the same ANCOVA model as in primary analysis. Differences between least squares means for (i) test product and no treatment regimen; (ii) positive control and no treatment regimen will be presented, together with 95% confidence intervals. The normality assumption for ANCOVA will be checked. If violated, non-parametric method such as Wilcoxon rank sum test may be applied.

The sebumeter and sebumeter excretion rate changes from baseline at Weeks 1, 4 and 8 will be analysed at each post-baseline visit using ANCOVA with treatment main effect, age stratum (<21, ≥21 years of age) and baseline count as covariate. Differences between least squares means for (i) test product and no treatment regimen; (ii) positive control and no treatment regimen will be presented, together with 95% confidence intervals (Table 14.2.3.1 for sebumeter, Table 14.2.4.1 for sebumeter excretion rate). The normality assumption for ANCOVA will be checked. If violated, non-parametric method such as Wilcoxon rank sum test may be applied.

Clinical assessment of blemish counts (papules and pustules) change from baseline at Weeks 1, 4 and 8 will be analysed at each post-baseline visit using ANCOVA with treatment main effect, age stratum (<21, ≥21 years of age) and baseline count as covariate. Differences between least squares means for (i) test product and no treatment regimen; (ii) positive control and no treatment regimen will be presented, together with 95% confidence intervals (Table 14.2.5.1 for the ITT population and Table 14.2.5.4 for the PP population). The normality assumption for ANCOVA will be checked. If violated, non-parametric method such as Wilcoxon rank sum test may be applied. A figure will be provided for blemish profile of the ITT population (Figure 14.2.1).

The summary and analysis of lay person image assessment will be performed for polarised images and non-polarised images separately. Proportion of subjects evaluated as 'Week 8 is better' will be tabulated by treatment group and rater. Data from all 24 raters will also be pooled and a repeated measure logistic regression will be applied including effects of treatment and age stratum and exchangeable correlation structure among repeats. Odds ratio between (i) test product and no treatment regimen; (ii) positive control and no treatment regimen will be provided together with its 95%CI (Table 14.2.6.1 for polarised image, Table

14.2.7.1 for non-polarised image). This analysis will not be performed if all subjects are judged by all raters as 'Week 8 is better'.

4.5.2 Pharmacokinetic (Secondary)

Not applicable.

4.6 Analysis of Safety

4.6.1 Adverse Events and Serious Adverse Events

All adverse events (AEs) will be summarised by system organ class and preferred term.

Treatment emergent adverse events (TEAEs), defined as the AEs reported after study product application (for the untreated group, TEAE is defined as first application of the standard cleanser), will be summarized by treatment and overall including the number and percentage of subjects having AEs and total number of AEs in each SOC and preferred term (Table 14.3.1.1). TEAEs will also be tabulated by severity (Table 14.3.1.2). Treatment-related TEAEs will be summarized and presented in the same manner (Table 14.3.1.3, Table 14.3.1.4).

Deaths occurring during treatment (if any) will be listed (Listing 14.3.2.1) by treatment, including the date and study day of death, and the principal cause of death. Non-fatal serious adverse events and TEAEs causing study treatment discontinuation will be listed (Listing 14.3.2.2, 14.3.2.3).

All AEs will be listed in the Listing 16.2.7.1 for randomised subjects and Listing 16.2.7.2 for non-randomised subjects.

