All efficacy analyses will be performed on the ITT population defined as all subjects randomized with at least one post-baseline study assessment. Safety analyses will be based on the safety population defined as all treated subjects. For the no treatment

Document Name	Rainbow Clinical Protocol.doc		
Туре	Version	Document Identifier	Effective Date
eldo controlled	4.0; Most-Recent; Effective; CURRENT	090032d580d464b0	23-May-2017 08:33:00
Reason For Issue	Auto Issue		

regimen, treatment is defined as at least one use of the washout cleanser postrandomisation. No statistical comparison between the positive control regimen and the test product regimen is planned.

The change from baseline in Corneometer measurement at 8 hours post-treatment on Day 1 (primary endpoint) will be summarized by age stratum, treatment regimen and study visit using means and 95% confidence intervals and compared between treatment regimen using analysis of covariance (ANCOVA) with treatment main effect, age stratum (<21, ≥21 years of age) and baseline measurement as covariate or Wilcoxon rank sum test, depending on the data distribution. Differences between least squares means for the test product and no treatment regimen will be presented, together with 95% confidence intervals. While for this proof of concept study statistical significance (p<0.05) may not be achieved, these results will drive sample size projections for future studies.

The secondary Corneometer and Sebumeter changes from baseline will be summarized by age stratum, treatment regimen and study visit and analysed using the ANCOVA model described above.

Clinical assessment of blemish counts (papules and pustules) will be summarized by age group stratum ($<21, \ge 21$ years of age), treatment regimen and study visit and compared between treatment regimens using means and 95% confidence intervals and compared between treatment regimen using analysis of covariance (ANCOVA) with treatment main effect, age stratum ($<21, \ge 21$ years of age) and baseline count as covariate or Wilcoxon rank sum test, depending on the data distribution. Differences between least squares means for the test product and no treatment regimen will be presented, together with 95% confidence intervals.

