7.2. Recording Adverse Events and Serious Adverse Events

Recording of adverse events and serious adverse events:

- 1. The investigator or site staff will be responsible for detecting, documenting and reporting events that meet the definition of an AE or SAE.
- 2. The investigator or site staff will then record all relevant information regarding an AE/SAE in the CRF.
- 3. There may be instances when copies of medical records for certain cases are requested by GSK. In this instance, all subject identifiers, with the exception of the subject number, will be blinded on the copies of the medical records prior to submission to GSK.
- 4. The investigator will attempt to establish a diagnosis of the event based on signs, symptoms, and/or other clinical information. In such cases, the diagnosis will be documented as the AE/SAE and not the individual signs/symptoms. Clinical AEs will be described by diagnosis and not by symptoms when possible (e.g., upper respiratory tract infection, seasonal allergy, etc. instead of runny nose).
- 5. AEs will be collected from the start of the washout product and until 5 days following last administration of the study product.
- 6. SAEs will be collected over the same time period as stated above for AEs. However, any SAEs assessed as **related** to study participation (e.g., investigational product, protocol mandated procedures, invasive tests, or change in existing therapy) or related to a GSK concomitant medication will be recorded from the time a subject consents to participate in the study up to and including any follow-up contact.
- 7. Medical conditions reported prior to the time period for reporting AEs/SAEs should be recorded as part of the subject's medical history.

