9.2.1. Definition of Analysis Populations

The 'Intent to treat' (ITT) population includes all subjects who are randomised into the study and have at least one post-baseline measurement available. All efficacy analyses will be based on the ITT population.

The Per Protocol (PP) population will consist of the subset of ITT subjects which excludes those subjects with significant protocol deviations. Protocol deviations will

Document Name	Rainbow Clinical Protocol.doc		
Туре	Version	Document Identifier	Effective Date
eldo controlled	4.0; Most-Recent; Effective; CURRENT	090032d580d464b0	23-May-2017 08:33:00
Reason For Issue	Auto Issue		

be identified prior to database unblinding and will include, but not be limited to, non-compliance with the protocol or product application and use of prohibited concomitant medications. Confirmatory analyses of at least the primary efficacy endpoint will be performed on the PP population.

The Safety population will include all subjects who applied any of the study products. All safety analyses will be performed using the Safety population. For the no treatment regimen, this will include any use of the cleanser post-randomisation.

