1.3 Treatments

	Washout/ Standard Cleanser	Test Product	Positive Control Cleanser	Positive Control Moisturiser
Product Name	Simple Kind to Skin Moisturising Facial Wash	Moisturising Cream with Niacinamide	Neutrogena Visibly Clear Spot Clearing Facial Wash	Vivatinell Acnecinamide Gel Cream
Product Formulation Code (MFC)	Commercially Available (UK)	CCI	Commercially Available (UK)	Commercially Available (Turkey)
Application Quantity	Approx. 0.6 g	Approx. 0.6 g	Approx. 0.6 g	Approx. 0.6 g
Application Instructions	Use twice daily (morning and night) with at least 8 hours	Use twice daily (morning and night) with at least 8 hours	Use twice daily (morning and night) with at least 8 hours	Use twice daily (morning and night) with at least 8 hours
	between product applications.	between product	between product applications.	between product applications.

Washout/ Standard Cleanser	Test Product	Positive Control Cleanser	Positive Control Moisturiser
Wet your face	applications.	Wet your face	Apply a
and hands with	Dispense two	and hands with	peasized
water. Dispense	pumps of	water. Dispense	quantity to your
the product into	product onto	the product into	whole face,
your hands and	your fingertips	your hands and	covering all
apply to the	and apply to	apply to the	blemishes.
face. Massage	your whole	face. Massage	Avoid contact
gently. Rinse	face, covering	gently. Rinse	with eyes. If
with water and	all blemishes.	with water and	contact occurs,
pat dry. Avoid	Avoid contact	pat dry. Avoid	rinse thoroughly
contact with	with eyes. If	contact with	with water.
eyes. If contact	contact occurs,	eyes. If contact	
occurs, rinse	rinse	occurs, rinse	
thoroughly with	thoroughly	thoroughly with	
water.	with water.	water.	

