3.3 Timepoints and Visit Windows

Deviations from the scheduled assessment times should be avoided or kept to a minimum as possible. Any deviation will be noted in the blinded data review before database lock and subjects may be considered for exclusion from the per protocol population.

The following are the assessment time windows.

Visit	Time window
Visit 2	5-7 days after Visit 1. Visit 2 is baseline and counted as Day 1.
Visit 3	Day 8 ± 1 Day

Visit	Time window
Visit 4	$Day 29 \pm 2 Days$
Visit 5	Day 57 ± 2 Days

Acute corneometer assessments will be taken 1 hour \pm 15 MINUTES, 3 hours \pm 15 MINUTES and 8 hours \pm 15 MINUTES after application of the cream for subjects randomised to the test product and positive control regimens and after cleansing for subjects randomised to the untreated regimen.

Sebumeter kinetic measurements will be taken 5 ± 1 minutes and 90 ± 5 minutes after forehead cleansing.

4 Data Analysis

Data analysis will be performed by inVentiv Health Clinical. Prior to database closure a Blind Data Review Meeting (BDRM) will be conducted in which various aspects of the trial will be discussed and agreed. The statistical analysis software used will be SAS version 9.4.

Unless otherwise described below, all listings will be produced for all randomized subjects.

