4.1.3 Analysis Populations

Six analysis populations are defined.

Population	Definition / Criteria	Analyses Evaluated
All Screened	All subjects those who are screened	Disposition
Subjects		
Randomised	All subjects who are randomised and may or	Protocol deviations
	may not receive the application of the study	
	products.	
Safety	Safety population includes all subjects who	Safety analysis
	are randomised and receive at least one dose	
	of study product. For the no-treatment	
	regimen, this will include any use of the	
	cleanser post-randomisation.	
Intent-to-Treat	The 'Intent to treat' (ITT) population	Efficacy analysis
(ITT)	includes all subjects who are in safety	
	population and have at least one post	
	baseline efficacy assessment.	
Per-Protocol	The Per Protocol (PP) population will consist	Efficacy analyses for
(PP)	of the subset of ITT subjects which excludes	corneometry and
	those subjects with major protocol	blemish count will also
	deviations.	be performed on the PP
		population

The numbers of subjects included in each of the analysis populations, and the number excluded from each population broken down by the reason for exclusion will be presented (Table 14.1.3). Subjects excluded from any of the analysis populations will be listed (Listing 16.2.3.1).

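### SAP 4.6.1 classes adverse events as treatment-emergent by when they are reported, not when they begin, so a washout-onset event first mentioned after application at Visit 2 qualifies

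*SAP*

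**What the plan says.** SAP 4.6.1 contains the only definition of a treatment-emergent adverse event (TEAE) that I can find in either document: "Treatment emergent adverse events (TEAEs), defined as the AEs reported after study product application". A parenthesis adds "for the untreated group, TEAE is defined as first application of the standard cleanser". Neither clause refers to onset or worsening. Protocol 9.3.4 asks for a TEAE summary without defining the term.

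On collection, protocol 7.2 states: "AEs will be collected from the start of the washout product and until 5 days following last administration of the study product". SAP 3.3 places Visit 2 "5-7 days after Visit 1. Visit 2 is baseline and counted as Day 1". The schedule of events has no adverse event step at Visit 1. In the synopsis list for Visit 2, supervised application is item 13 and adverse events are item 15; protocol 6.2.13 and 6.2.15 follow the same order. The scripted question in protocol 7.4 offers several look-back periods, one of which reaches back to the previous visit.

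TEAEs feed Tables 14.3.1.1 to 14.3.1.4. Listing 16.2.7.1 shows start date, study day and start time for every adverse event in randomised subjects.

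**The concern.** A TEAE table is meant to show what began, or got worse, once randomised treatment started. A rule that turns on reporting time answers a different question when collection starts 5 to 7 days before treatment and the first scheduled enquiry is listed after the first application. An event from the washout can then appear in the TEAE tables against a regimen that the subject had not yet begun. Whether it appears can depend on which step of Visit 2 brought it to light.

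Safety is a stated secondary objective, and the summary tables, unlike the listing, give the reader no means of separating such events.

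**Working it through.** The plan gives no figure to reproduce. The first part of the check is textual.

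**Tracing one event.** Take an event with onset in the washout, after first use of the washout product.

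1. It is an adverse event. Protocol 7.1.1 covers the washout product, and 7.2 opens collection at the start of washout.
2. It cannot have been recorded at a Visit 1 adverse event step, because there is none.
3. If the subject first mentions it at Visit 2 item 15, taken in the listed order, the report follows application (item 13). It meets the SAP 4.6.1 wording and is a TEAE.
4. If it surfaces at Visit 2 items 1 to 3 (medication, diary review, continued eligibility), the report precedes application. On the same wording it is not a TEAE.
5. Under an onset rule it is not a TEAE by either route, unless it worsens after treatment starts.

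The error runs one way. An event that starts after application must also be reported after it, so the rule can add pre-treatment events but cannot lose post-treatment ones.

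The same SAP uses a date rule elsewhere: section 4.3.2 separates prior from concomitant medication by stop and start relative to the baseline administration.

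**Illustrative size.** Inputs:
- *w*, washout length: 5 to 7 days (SAP 3.3).
- *T*, post-treatment window: 56 days of use (protocol 3.4), or 56 + 5 = 61 days with the collection tail in protocol 7.2.
- *f*, the fraction of washout events first reported at item 15: not in the documents, assumed.
- Event rate: assumed constant over washout and treatment.

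Share of counted TEAEs that began in washout = *fw* / (*fw* + *T*).

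| *f* | *T* (days) | *w* = 5 | *w* = 7 |
|---|---|---|---|
| 1 | 61 | 5/66 = 7.6% | 7/68 = 10.3% |
| 1 | 56 | 5/61 = 8.2% | 7/63 = 11.1% |
| 0.5 | 61 | 2.5/63.5 = 3.9% | 3.5/64.5 = 5.4% |
| 0.5 | 56 | 2.5/58.5 = 4.3% | 3.5/59.5 = 5.9% |

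**Between-arm difference.** Washout precedes randomisation, so the expected washout rate is the same in every arm. Assume true 61-day incidences of 20% and 10%, *f* = 1, and washout events at the lower arm's rate in both arms. The proportion free of any counted event is then multiplied in each arm by 0.9^(*w*/61).
- *w* = 5: factor 0.991. Incidences 1 − 0.8 × 0.991 = 20.7% and 1 − 0.9 × 0.991 = 10.8%; difference 9.9 points.
- *w* = 7: factor 0.988. Incidences 21.0% and 11.1%; difference 9.9 points.

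The true difference is 10.0 points. With 132/3 = 44 subjects per arm, each arm gains about 0.3 to 0.5 subjects with a TEAE.

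**The case against.** The strongest reply is that this is loose wording that nobody would program literally. The visible adverse event listing has start and end dates and times but no report time. Sorting events by the Visit 2 step that caught them would need a within-visit report time that no visible display carries, so the workable derivation compares onset with first treatment. That is a fair inference about what the programmers may have done. The eCRF is not visible, however, and the SAP states a different rule.

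Three limits stand:
- Only Visit 5 is said to run in the listed order, so adverse events at Visit 2 might be asked about before application. The scripted question also has shorter look-back options, and diary entries that qualify must be recorded. All of this lowers the frequency; none of it supplies an onset rule.
- The visible shell for Table 14.3.1.1 has no onset footnote, but the copy breaks off within Table 14.3.1.2. Notes on the remaining shells cannot be checked.
- Adverse event analysis is descriptive, and the full listing lets a reader pick out pre-treatment onsets.

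A reader might also infer that the untreated arm's clock starts in washout. The parenthesis does not say post-randomisation, SAP 1.3 heads one column "Washout/ Standard Cleanser", and the synopsis says "treatment is defined as at least one use of the washout cleanser postrandomisation". The documents do not support that reading. Protocol 3.4 and 5.2 place the first application of the standard cleanser at the site, in the test phase. Protocol 5.8 and 6.2.12 treat the two cleansers as separately labelled supplies, one returned before the other is dispensed. The synopsis phrase carries its own post-randomisation qualifier, as do the Safety population definitions in protocol 9.2.1 ("For the no treatment regimen, this will include any use of the cleanser post-randomisation") and SAP 4.1.3 ("cleanser post-randomisation").

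**Conclusion.** The definition in SAP 4.6.1 lacks an onset criterion and, followed as written, can count washout-onset events as treatment-emergent. That conclusion rests on the text alone.

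The size does not. The number of affected events cannot be derived from the documents. The figure of about 8% to 11% of counted TEAEs assumes a constant event rate and that every washout event is first reported at the Visit 2 adverse event step. It is neither an expected value nor a strict upper bound: halving the reported fraction roughly halves it, and a higher event rate in washout would raise it.

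A reader might infer a bias towards one arm. The documents do not support that: one rule covers all three arms, and washout precedes randomisation. Absolute TEAE rates would be slightly inflated and differences nearly unchanged, provided that allocation does not affect whether a subject mentions a washout event. This is a low-severity point, worth correcting because the correction is cheap.

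**What to change.** Replace the definition in SAP 4.6.1 with an onset rule: a TEAE is an adverse event whose onset, or worsening in severity, falls at or after the first post-randomisation product use at Visit 2. That first use is the supervised cleanse in protocol 6.2.13, which is common to all three arms.

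Derive it from the start date and start time already in Listing 16.2.7.1. The time is needed for Day 1, when application and the adverse event step share a date. State how a missing Day 1 start time is handled. List washout-onset events in randomised subjects separately, with a flag. If the programs already use onset, say so in the SAP.

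The cost is one sentence and one listing flag, with no new data. SAP Addendum 1 shows that the study has been unblinded, so a change made now should be documented as post-unblinding.
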